10.1.10. Protocol Deviations

A protocol deviation is any noncompliance with the clinical trial protocol, GCP, or other study requirements (e.g., SOPs, Laboratory Manuals, etc). The noncompliance may be either on the part of the subject, the investigator, or the study site staff. As a result of deviations, corrective actions are to be developed by the site and implemented promptly.

These practices are consistent with ICH E6:

- 4.5 Compliance with Protocol, sections 4.5.1, 4.5.2, and 4.5.3
- 5.1 Quality Assurance and Quality Control, section 5.1.1
- 5.20 Noncompliance, sections 5.20.1, and 5.20.2.

It is the responsibility of the site to use continuous vigilance to identify and report deviations within 5 working days of identification of the protocol deviation, or within 5 working days of the scheduled protocol-required activity. All deviations must be addressed in study source documents and reported to the clinical study monitor or to the CRO. Protocol deviations must be sent to the IRB/EC per their guidelines. The site investigator/study staff is responsible for knowing and adhering to their IRB/EC requirements.

It is not anticipated that waivers of eligibility requirements will be granted for any subjects. However, if eligibility requirements are waived in special circumstances, waivers must be approved by the medical monitor and the sponsor before a subject may be enrolled. Documentation of granted waivers will be maintained in the investigator's and sponsor's files.

10.1.11. Publication and Data Sharing Policy

The results of this study may be published or presented at scientific meetings. The investigator agrees to submit all manuscripts or abstracts to Botanix Pharmaceuticals at least 30 days prior to submission. This allows Botanix Pharmaceuticals to protect proprietary information and to provide comments based on information from other studies that may not yet be available to the investigator.

In accordance with standard editorial and ethical practice, Botanix Pharmaceuticals will generally support publication of multicenter trials in their entirety. In this case, a coordinating investigator will be designated by mutual agreement. Authorship will be determined by mutual agreement.

10.2. Conflict of Interest Policy

The independence of this study from any actual or perceived influence is critical. Therefore, any actual conflict of interest of persons who have a role in the design, conduct, analysis, publication, or any aspect of this trial will be disclosed and managed. Furthermore, persons who have a perceived conflict of interest will be required to have such conflicts managed in a way that is appropriate to their participation in the study. The study leadership has established policies and procedures for all study group members to disclose all conflicts of interest and will establish a mechanism for the management of all reported dualities of interest.

10.3. List of Abbreviations

| | |
|------|-----------------------------------------|
| AE | Adverse Event |
| ATC | Anatomical Therapeutic Chemical |
| BID | Twice Daily |
| CBC | Complete Blood Count |
| CBD | Cannabidiol |
| CFR | Code of Federal Regulations |
| CI | Confidence Interval |
| CMP | Clinical Monitoring Plan |
| CRA | Clinical Research Assistant / Associate |
| CRO | Clinical Research Organization |
| DSMB | Data Safety Monitoring Board |
| EC | Ethics Committee |
| eCRF | Electronic Case Report Form |
| EDC | Electronic Data Capture |
| FDA | Food & Drug Administration |

| | |
|--------|----------------------------------------------|
| GCP | Good Clinical Practices |
| GMP | Good Manufacturing Practices |
| IGA | Investigator's Global Assessment |
| IND | Investigational New Drug |
| IRB | Institutional Review Board |
| MCH | Mean Corpuscular Haemoglobin |
| MCHC | Mean Corpuscular Haemoglobin Concentration |
| MCV | Mean Corpuscular Volume |
| MedDRA | Medical Dictionary for Regulatory Activities |
| NSAID | Non-Steroidal Anti-inflammatory Drug |
| OTC | Over the Counter |
| PK | Pharmacokinetics |
| QA | Quality Assurance |
| QC | Quality Control |
| RBC | Red Blood Cell |
| SAE | Serious Adverse Event |
| SAP | Statistical Analysis Plan |
| SAS | Statistical Analysis System |
| SD | Standard Deviation |
| SOP | Standard Operating Procedure |
| TEAE | Treatment Emergent Adverse Event |
| THC | Tetrahydrocannabinol |
| UDS | Urine Drug Screen |
| UPT | Urine Pregnancy Test |
| WBC | White Blood Cell |
| WHO | World Health Organization |
| WOCBP | Women of Child-Bearing Potential |

1. LIST OF ABBREVIATIONS AND DEFINITIONS OF TERMS

AE(s)	adverse event(s)
ANCOVA	analysis of covariance
ATC	anatomical therapeutic chemical
AUS	Australia
BP	blood pressure
BPM	beats per minute
cm	centimeters
CRF(s)	case report form(s)
eCRF(s)	electronic case report form(s)
FDA	Food and Drug Administration
GCP	good clinical practice
HEENT	head, eyes, ears, nose, and throat
HR	heart rate
hr(s)	hour(s)
ICH	International Conference on Harmonization
ITT	intent-to-treat
kg	kilograms
LOCF	last observation carried forward
LSMean or LSM	least squares mean
max	maximum
MedDRA	Medical Dictionary for Regulatory Activities
mg	milligram
min	minimum
n	number of observations
N	number of subjects (sample size)
PP	per-protocol
PT	preferred term
QST	QST Consultations, Ltd.
SAE(s)	serious adverse event(s)
SAS®	Statistical Analysis System (SAS® Institute Inc., Cary, NC)
SD	standard deviation
SOC	system organ class

TEAE(s)	treatment-emergent adverse event(s)
TEMP	temperature
US	United States
WHO	World Health Organization
WHO-DDE	World Health Organization Drug Dictionary

2. INTRODUCTION

Acne is the most common skin disease in the world and is characterized by partial obstruction of the pores and associated local skin lesions that can appear on the face, chest or back [1, 2]. Obstructed pores can become enlarged and inflamed as sebum and its breakdown products accumulate, resulting in visible lesions that can be unsightly and cause permanent scarring [1, 2]. Acne usually begins in puberty and affects many adolescents and young adults, but it can occur at any stage of life. Approximately 85 percent of people between the ages of 12 and 24 experience at least minor acne [3]. Acne often causes significant physical and psychological problems such as permanent scarring, poor self-image, depression and anxiety [4].

Botanix Pharmaceuticals' BTX 1503 containing the active pharmaceutical ingredient, cannabidiol (CBD) in a topical liquid formulation, is being developed for the treatment of acne vulgaris. CBD is a member of a broader family of compounds known as cannabinoids, a class of compounds originally derived from the *cannabis sativa* plant [5].

No known well-controlled, human clinical studies have ever been conducted using CBD to treat skin disease, and no CBD containing pharmaceuticals have been approved to treat skin disease. Researchers have found that CBD may play a beneficial role in regulating the cutaneous endocannabinoid system by decreasing unwanted skin cell growth, sebum production and skin inflammation associated with many human skin diseases [5].

BTX 1503 is a formulation of active synthetic CBD and inactive excipients designed to deliver a consistent dose of CBD to directly treat patients with acne. It is considered that CBD may:

- normalize excessive lipid synthesis of human sebocytes;
- decrease proliferation (but not the viability) of these human sebocytes;
- inhibit hyperproliferation of keratinocytes;
- exert anti-inflammatory actions; and
- have anti-bacterial effects [5, 6].

This study is designed to investigate the efficacy, safety and tolerability of BTX 1503 in subjects with moderate to severe acne.

3. STUDY OBJECTIVES

The objective of this study is to assess safety and efficacy of various doses of BTX 1503 liquid formulation in subjects with moderate to severe acne vulgaris of the face.

4. STUDY DESIGN

4.1 Overall Study Design

This will be a multi-center, randomized, double-blind, vehicle-controlled, parallel group, dose-finding study in pediatrics, adolescents, and adults (aged 12 to 40 years). Approximately 360 subjects will be enrolled.

There will be five dose groups. All subjects will apply study drug for 84 days.

- BTX 1503 5% twice daily (BID),
- BTX 1503 5% once daily (QD),
- BTX 1503 2.5% once daily (QD),
- Vehicle BID, or
- Vehicle QD.

At the Baseline visit, qualified subjects will be randomized to treatment using an Interactive Web-based Randomization System (IWRS). The study will be a total of up to 17 weeks in duration; screening period up to 35 days (5 weeks) and 84 days (12 weeks) of treatment. During the study subjects will return to the study clinic at Day 14, 28, 56, and 84 (Study Exit).

4.1.1 Schedule of Visits and Assessments

The schedule of assessments can be found in Section 7.3.8 of the protocol.

4.1.2 Method of Assigning Subjects to Treatment Groups

A randomization schedule will be generated by a member in the QST Consultations, Ltd. (QST) Statistical Services department who is not associated with the conduct or analysis of the study, using a validated system. The randomization list will not be stratified, but stratification by site will be accomplished within the Interactive Web-based Randomization System (IWRS).

Once a subject is deemed eligible to enroll, randomization will occur using an IWRS. The IWRS will assign a study drug kit number based on a predetermined randomization schedule. The kit number will be recorded in the electronic case report form (eCRF). Randomization will be 2:2:2:1:1 (90 subjects in each active group and 45 in each vehicle group) and done by site.

4.1.3 Blinding

The Sponsor, the CRO, the investigator, study site personnel and subjects will be blinded to the treatment assignment. The randomization schedule will be kept strictly confidential and accessible only to authorized persons. Only when the study has been completed, the protocol violations determined, and the study database locked will the randomization schedule be made available for analysis.

During the study, the randomization code will not be broken except in the case of a safety concern, either for an individual subject or for the entire study. If a subject has an adverse event (AE) that may necessitate unblinding of the randomization code, the site will contact the CRO and sponsor to discuss if there are options other than unblinding. If the site and sponsor agree that unblinding is in the best interests of the subject, the IWRS system will be used to obtain treatment assignment information. The Medical Monitor must be notified whenever study medication is unblinded, preferably prior to unblinding a subject.

5. EFFICACY AND SAFETY ENDPOINTS

5.1 Efficacy Endpoints

For all efficacy evaluations the measurement endpoint is defined at Day 84.

5.1.1 Primary Efficacy Endpoint

The primary efficacy endpoint for the study is:

- Absolute change from Baseline in inflammatory lesion counts at Day 84.

5.1.2 Secondary Efficacy Endpoints

The secondary efficacy endpoints for the study are:

- Absolute change from Baseline in non-inflammatory lesion counts at Day 84,
- The percent change from Baseline in the inflammatory lesion counts at Day 84,
- The percent change from Baseline in the non-inflammatory lesion counts at Day 84,

- The proportion of subjects with at least a 2-grade reduction from the Baseline IGA score at Day 84,
- The proportion of subjects with an IGA score of “clear” or “almost clear” at Day 84, and
- The proportion of subjects with an IGA score of “clear” or “almost clear” at Day 84 and at least a 2-grade reduction from the Baseline IGA score.

5.1.3 Exploratory Efficacy Endpoints

The exploratory efficacy endpoints are:

- The change from Baseline in the total lesion count at Day 84,
- The percent change from Baseline in the total lesion count at Day 84,
- The change from Baseline in the IGA scores at Day 84,
- The absolute and percent change from Baseline in inflammatory, non-inflammatory, and total lesion counts at Day 14, Day 28, and Day 56,
- The proportion of subjects with an IGA score of “clear” or “almost clear” at Day 14, Day 28, and Day 56,
- The proportion of subjects with at least a 2-grade reduction from the Baseline IGA score at Day 14, Day 28, and Day 56,
- The proportion of subjects with an IGA score of “clear” or “almost clear” at Day 14, Day 28, and Day 56 and at least a 2-grade reduction from the Baseline IGA score,
- The change from Baseline in the Acne-QoL at Day 84, and
- Subject’s assessment of the change in their acne from Baseline to Day 84 (Patient Reported Outcome [PRO]).

5.2 Safety Endpoints

Safety will be assessed through adverse events (AEs), cutaneous tolerability (erythema, scaling, dryness, pruritus, and burning/stinging), complete blood count (CBC), chemistry, and urinalysis laboratory testing, and physical exam.

6. STATISTICAL AND ANALYTICAL PLANS

6.1 General Methodology

All statistical processing will be performed using SAS® 9.3 or higher. No interim analyses are planned. This Phase 2 study is designed to identify the response to two different dosing frequencies and two concentrations of BTX 1503. Statistical tests applied to the outcomes will be exploratory. No adjustments for Type I error will occur.

Descriptive statistics will be used to provide an overview of the efficacy and safety results. For categorical parameters, the number and percentage of subjects in each category will be presented. For continuous parameters, descriptive statistics will include n (number of subjects), mean, standard deviation (SD), median, minimum and maximum.

The primary method of handling missing efficacy data in the ITT analysis set will be based on last observation carried forward (LOCF). Repeated measures analyses will be used on the observed data as a sensitivity analysis on the primary endpoint and the first secondary endpoint.

The efficacy analysis performed on the ITT population is considered the primary analysis. The efficacy analysis performed on the per-protocol (PP) population is considered supportive analysis.

The number of subjects in each analysis set will be summarized. Reasons for study withdrawal during the study will be summarized using frequencies and percentages by treatment group.

Reported AEs, medical history terms, and prior and concomitant procedures and therapies will be classified on the basis of Medical Dictionary for Regulatory Activities (MedDRA) terminology. Prior and concomitant medications will be classified on the basis of World Health Organization Drug Dictionary (WHO-DDE) terminology.

6.1.1 Statistical Analysis

All analyses will be performed by QST using SAS® Version 9.3 or later. All summary tables and data listings will be prepared utilizing SAS® software.

The standard operating procedures (SOPs) of QST will be followed in the creation and quality control of all data displays and analyses.

6.1.2 Baseline Definition

Baseline is defined as the last non-missing assessment prior to first application of study drug.

6.1.3 Visit Windowing

Data will be summarized based on nominal visit indications with the exception of data captured at early termination and unscheduled visits. Data from early termination and unscheduled visits will be summarized based on mapped visit values. The analysis windows for early termination and unscheduled visits are presented in the following table.

Analysis Windows

Scheduled Visit	Target Study Day	Window (Days)
Day 14	15	9 to 21
Day 28	29	22 to 42
Day 56	57	43 to 70
Day 84	85	71 to 98

Data collected at early termination and unscheduled visits prior to study day 9 will not be analyzed, with the exception of those identified as baseline values. Data collected at early termination and unscheduled visits after study day 98 will not be included in analyses.

The definition for the study day included in each study window is defined as below:

Study Day prior to Day 1 = Visit Date – Day 1 Date

Study Day on or after Day 1 = Visit Date – Day 1 Date + 1

If an assessment's mapped visit is a visit at which the subject has data from a scheduled visit present, or if no analyses are planned for the assessment at the mapped visit, the data collected at the early termination or unscheduled visit will not be included in analyses.

In the event of multiple values from unscheduled or early termination assessments within an analysis window, the value closest to the scheduled visit target study day will be used for analyses. If two values tie as closest to the time point (for example, one value is before and the other value is after the time point), then the later value will be selected.

Data collected at all visits will be included in the data listings with visit presented as reported by the site.

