7.3.8. Schedule of Events Table – Subjects with Acne Vulgaris

The Schedule of Events is provided in [Table 3](#).

Table 3: Time and Events Schedule

| Parameter | Screening Visit (-35 to Day 1) | Baseline Visit (Day 1)^a | Day 14 Visit (Day 14 ±3 days) | Day 28 Visit (Day 28 ±5 days) | Day 56 Visit (Day 56 ±5 days) | Day 84 Visit^c (Day 84 ±5 days) |
|---------------------------------------------------|-------------------------------------------|----------------------------------------------------------------------------------|------------------------------------------|------------------------------------------|------------------------------------------|------------------------------------------------------|
| | Visit 1 | Visit 2 | Visit 3 | Visit 4 | Visit 5 | Visit 6 |
| Written informed consent/assent | X | | | | | |
| Medical history/ review of systems | X | | | | | |
| Demographics with Height and Weight | X | | | | | |
| Tobacco and Alcohol History | X | | | | | |
| Urine pregnancy test (WOCBP only) | X | X | | X | X | X |
| Eligibility criteria review | X | X | | | | |
| Safety Laboratory (CBC, chemistry and urinalysis) | | X | | | | X |
| Urine drug screening | X | X | | | | |
| Investigator's Global Assessment | X | X | X | X | X | X |
| Inflammatory and non-inflammatory lesion count | X | X | X | X | X | X |
| Photography of Face (selected sites) | | X | | | | X |
| Administer Acne-QoL | | X | | | | X |
| Administer PRO | | | | | | X |
| Ensure compliance with study drug administration | | | X | X | X | X |
| Study drug administration by site personnel (am) | | X | | | | |
| Study drug administration by subject | | Day 1 pm to Day 84 ^d ; Day 14, 28, 56, and 84 doses applied in clinic | | | | |
| Concomitant medications | X | X | X | X | X | X |
| Adverse events | | X | X | X | X | X |
| Cutaneous tolerability assessments ^b | | X | X | X | X | X |
| Dispense study drug and diary | | X | | X | X | |
| Collect diary and study drug | | | | X | X | X |

^a Screening and Baseline Visit may occur on the same day.

^b Assess cutaneous tolerability prior to and approximately 15 min after initial dose on Day 1 and the subject applications on Day 14, Day 28, Day 56, and Day 84

^c If subject discontinues treatment early, Day 84 evaluations will be performed when possible.

^d Subjects randomized to BID dosing will apply study drug in the morning and evening, 8 to 12 hours apart.

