9.4.2. Safety Analyses

All subjects who receive at least one confirmed dose of study drug and have at least one post-Baseline assessment will be included in the safety analyses.

All treatment-emergent adverse events (TEAEs) reported during the study will be recorded and classified based on MedDRA terminology. Treatment-emergent adverse events are those AEs with an onset on or after the first application of study medication. All reported TEAEs will be summarized by treatment group, the number of subjects reporting events, system organ class, preferred term, severity, relationship to study drug, and seriousness. When summarizing events by causality and severity, each subject will be counted only once within a system organ class or a preferred term by using the event with the greatest relationship and highest severity within each classification.

Serious adverse events (SAEs) will be summarized by cohort, system organ class, preferred term, severity, outcome and relationship to study drug; and all SAEs will be listed by subject. In addition, a list of subjects who prematurely discontinue from the study due to an AE and the reason for discontinuation will be provided.

Concomitant medication will be mapped to ATC Level 2 using the WHODrug dictionary. The number and percentage of subjects reporting each medication will be summarized. Medications taken by each subject will be listed.

Changes from Baseline in safety laboratory assessments (CBC, chemistry and urinalysis) at Day 84 will be summarized using shift tables. Abnormal values will be summarized. Laboratory values will be listed by subject.

Cutaneous tolerability will be assessed at the Baseline, Day 14, Day 28, Day 56 and Day 84 Visits. Summaries will present frequencies and percentages for the grading of each of the signs/symptoms that was performed at each scheduled visit/time point combination. The summary of cutaneous tolerability assessment scores table will present summary statistics for the scores ('None'=0, 'Slight'=1, 'Moderate'=2 and 'Severe'=3) and the change from Baseline values at each scheduled post-Baseline visits/time point for each of the signs/symptoms. Listings will be provided by subject.

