6.10.3 Clinical Laboratory Evaluation

Laboratory test results will be summarized with descriptive statistics at Baseline and Day 84. Additionally, shifts from Baseline to Day 84 in laboratory test results based on normal ranges will be summarized with frequency counts and percentages. Individual laboratory test results as well as pregnancy test results will be presented in a by-subject listing.

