6.10.4 Other Observations Related to Safety

6.10.4.1 Cutaneous Tolerability Assessments

Cutaneous tolerability (erythema, scaling, dryness, pruritus, and burning/stinging) will be summarized at each visit using counts and percentages by treatment group. In addition, worst post-Baseline grade will be summarized by treatment group using counts and percentages. Any incident of mild, moderate, or severe post-Baseline results will be summarized by treatment group using counts and percentages.

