None	xx (xx.x%)	xx (xx.x%)	xx (xx.x%)	xx (xx.x%)	xx (xx.x%)	xx (xx.x%)	xx (xx.x%)
Day 1 – 15 Mins Post-Dose							
n	xx	xx	xx	xx	xx	xx	xx
Severe	xx (xx.x%)	xx (xx.x%)	xx (xx.x%)	xx (xx.x%)	xx (xx.x%)	xx (xx.x%)	xx (xx.x%)
Moderate	xx (xx.x%)	xx (xx.x%)	xx (xx.x%)	xx (xx.x%)	xx (xx.x%)	xx (xx.x%)	xx (xx.x%)
Mild	xx (xx.x%)	xx (xx.x%)	xx (xx.x%)	xx (xx.x%)	xx (xx.x%)	xx (xx.x%)	xx (xx.x%)
None	xx (xx.x%)	xx (xx.x%)	xx (xx.x%)	xx (xx.x%)	xx (xx.x%)	xx (xx.x%)	xx (xx.x%)
Day 14 – Pre-Dose							
n	xx	xx	xx	xx	xx	xx	xx
Severe	xx (xx.x%)	xx (xx.x%)	xx (xx.x%)	xx (xx.x%)	xx (xx.x%)	xx (xx.x%)	xx (xx.x%)
Moderate	xx (xx.x%)	xx (xx.x%)	xx (xx.x%)	xx (xx.x%)	xx (xx.x%)	xx (xx.x%)	xx (xx.x%)
Mild	xx (xx.x%)	xx (xx.x%)	xx (xx.x%)	xx (xx.x%)	xx (xx.x%)	xx (xx.x%)	xx (xx.x%)
None	xx (xx.x%)	xx (xx.x%)	xx (xx.x%)	xx (xx.x%)	xx (xx.x%)	xx (xx.x%)	xx (xx.x%)

[Repeat for Day 14 – 15 Mins Post-Dose, Day 56 – Pre-Dose, Day 56 – 15 Mins Post-Dose, Day 84 – Pre-Dose, and Day 84 – 15 Mins Post-Dose]

[Repeat for Pruritus, Erythema, Dryness, and Scaling]

Note: Percentages are based on the number of subjects in each treatment group in the Safety population with a non-missing assessment at the given visit.

SOURCE: USERNAME/SPONSOR/PROJECT/JOBNAME (DATE,TIME)

Table 14.3.0.2.2: Summary of Cutaneous Tolerability Assessments Worst Post-Baseline Grades
(Safety Population)
(Page x of y)

Worst Post-Baseline Grade	Vehicle QD (N=xx)	Vehicle BID (N=xx)	Vehicle Combined (N=xx)	BTX 1503 5% BID (N=xx)	BTX 1503 5% QD (N=xx)	BTX 1503 2.5% QD (N=xx)	BTX 1503 Combined (N=xx)
Burning/Stinging							
n	xx	xx	xx	xx	xx	xx	xx
Severe	xx (xx.x%)	xx (xx.x%)	xx (xx.x%)	xx (xx.x%)	xx (xx.x%)	xx (xx.x%)	xx (xx.x%)
Moderate	xx (xx.x%)	xx (xx.x%)	xx (xx.x%)	xx (xx.x%)	xx (xx.x%)	xx (xx.x%)	xx (xx.x%)
Mild	xx (xx.x%)	xx (xx.x%)	xx (xx.x%)	xx (xx.x%)	xx (xx.x%)	xx (xx.x%)	xx (xx.x%)
None	xx (xx.x%)	xx (xx.x%)	xx (xx.x%)	xx (xx.x%)	xx (xx.x%)	xx (xx.x%)	xx (xx.x%)
Pruritus							
n	xx	xx	xx	xx	xx	xx	xx
Severe	xx (xx.x%)	xx (xx.x%)	xx (xx.x%)	xx (xx.x%)	xx (xx.x%)	xx (xx.x%)	xx (xx.x%)
Moderate	xx (xx.x%)	xx (xx.x%)	xx (xx.x%)	xx (xx.x%)	xx (xx.x%)	xx (xx.x%)	xx (xx.x%)
Mild	xx (xx.x%)	xx (xx.x%)	xx (xx.x%)	xx (xx.x%)	xx (xx.x%)	xx (xx.x%)	xx (xx.x%)
None	xx (xx.x%)	xx (xx.x%)	xx (xx.x%)	xx (xx.x%)	xx (xx.x%)	xx (xx.x%)	xx (xx.x%)
Erythema							
n	xx	xx	xx	xx	xx	xx	xx
Severe	xx (xx.x%)	xx (xx.x%)	xx (xx.x%)	xx (xx.x%)	xx (xx.x%)	xx (xx.x%)	xx (xx.x%)

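### SAP 6.1.3 applies its early-termination and unscheduled-visit exclusions to safety data, so early-withdrawal labs and some extra-visit tolerability grades drop out of their tables

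*SAP*

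**What the plan says.** **The rule.** SAP 6.1.3 (Visit Windowing) stands under General Methodology and speaks of data and assessments in general. Scheduled visits keep their nominal label, but "Data from early termination and unscheduled visits will be summarized based on mapped visit values". The windows are study days 9–21 (Day 14), 22–42 (Day 28), 43–70 (Day 56) and 71–98 (Day 84). For early-termination and unscheduled visits:

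- "Data collected at early termination and unscheduled visits prior to study day 9 will not be analyzed", baseline values excepted; results after day 98 are also left out.
- A result is dropped if the subject already has scheduled data at the mapped visit.
- In addition, "if no analyses are planned for the assessment at the mapped visit, the data collected at the early termination or unscheduled visit will not" be used.
- Of several extra values in one window, only the one nearest the target day is kept (the later one if tied).

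All visits remain in the listings.

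**Labs.** SAP 6.10.3: "Laboratory test results will be summarized with descriptive statistics at Baseline and Day 84". Shift tables use the same two time points, with percentages based on subjects who have both. Protocol 7.2.1 schedules no other labs, and SAP 6.1.5 imputes only efficacy data. Protocol Table 3, footnote c: "If subject discontinues treatment early, Day 84 evaluations will be performed when possible". Protocol 9.4.2: "Abnormal values will be summarized".

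**Timing after early withdrawal.** Protocol 5.3.1 asks for the Day 84 assessments before withdrawal and also, if possible, at Day 84 ±5 days. Protocol 7.3.7 seeks the Day 84 ±5 return only when the reason for stopping is not an AE.

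**Tolerability.** SAP 6.10.4.1 says that "worst post-Baseline grade will be summarized by treatment group using counts and percentages". It also plans a count of any mild, moderate or severe result after baseline. Neither summary is limited by visit type.

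**The concern.** Windowing of this kind suits by-visit efficacy summaries, where each subject should contribute one value per visit. Applied to safety, it removes results from subjects who left early or needed an extra visit, and these are the results a safety summary most needs.

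For labs, the excluded sample may be the subject's only one after dosing. The subject stays in the Safety population count but leaves the shift-table denominator. For tolerability, a table headed as the worst grade would not always hold the worst grade recorded. Both documents justify the sample size by its adequacy for evaluating safety and tolerability, and Protocol 2.4.1 names local skin reactions as a risk, so these tables matter here.

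**Working it through.** The plan has no figure of its own to reproduce: neither document gives a dropout rate or a timing of dropout. The inputs are the SAP 6.1.3 windows, the lab time points in SAP 6.10.3 and the planned 360 subjects. Dropout rate, timing and return for Day 84 labs are assumptions.

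**1. Each possible early-termination sample day (study days 2–84) mapped to a visit**

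| Sample day | Number of days | Mapped visit | Lab analysis planned? | Result |
|---|---|---|---|---|
| 2–8 | 7 | none | – | excluded |
| 9–21 | 13 | Day 14 | no | excluded |
| 22–42 | 21 | Day 28 | no | excluded |
| 43–70 | 28 | Day 56 | no | excluded |
| 71–84 | 14 | Day 84 | yes | kept |

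Excluded: 7 + 13 + 21 + 28 = 69 of 83 days. Kept: 14 of 83.

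**2. Share of early dropouts affected, if each is sampled on leaving and none returns**

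- Even timing over days 2–84: 69/83 = 83%.
- Even timing over days 2–78 (before the Day 84 ±5 visit window opens at 84 − 5 = 79): 69/77 = 90%.
- Weight falling linearly (85 − day): 97%. Weight rising linearly (day): 70%.

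**3. Effect of a return at Day 84 ±5.** That is study days 79–89, or 80–90 around the SAP target of 85. Both lie inside 71–98, so those labs are kept. The even-timing share of 83–90% is multiplied by (1 − return rate):

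- 25% return: 62–67%
- 50% return: 42–45%
- 75% return: 21–22%

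**4. Subjects.** Assumed dropout of 10–20% of 360 is 36–72.

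- No return: 36 × 0.831 = 29.9 up to 72 × 0.896 = 64.5, about 30–65.
- Half return: 36 × 0.831 × 0.5 = 15.0 up to 72 × 0.896 × 0.5 = 32.3, about 15–32.

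**5. Tolerability: the two SAP sections side by side.** SAP 6.10.4.1 wants the worst grade and any reaction after baseline. Two illustrations show what SAP 6.1.3 does to them:

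- Severe burning is graded at an unscheduled visit on study day 5 and the subject does not come back. The day-5 grade is excluded. The 15-minute grade on Day 1, which may be none, becomes the worst grade.
- A worse grade is recorded at an extra visit on study day 18, after a scheduled Day 14 visit. Day 18 lies in the 9–21 window, which already has scheduled data, so the worse grade is dropped.

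**6. A separate slip in the shell.** The bracketed instruction for Table 14.3.0.2.1 reads "Repeat for Day 14 – 15 Mins Post-Dose, Day 56 – Pre-Dose, Day 56 – 15 Mins Post-Dose" and then continues to Day 84. Day 28 is missing, although Protocol 7.3.5 assesses it before and after dosing. That is 2 of 10 time points (5 visits × 2).

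**The case against.** The strongest reply is that exclusion depends on the day of the sample, not the day of stopping. Protocol 5.3.1 and 7.3.7 both aim for assessments at Day 84 ±5, and labs taken then are kept. This stands. A reader might infer that nearly all early dropouts, or everyone who stops by day 70, lose their labs from the tables; the documents do not support that. Subjects withdrawn for an AE remain the most exposed, because 7.3.7 does not cover them and 5.3.1 asks only if possible.

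Second, little is lost outright. TEAE tables go by onset date (SAP 6.10.2), Protocol 8.1.1 counts an abnormal lab finding as a possible AE, and listings hold every visit. This also stands, so the gap is confined to the lab summary and shift tables and the tolerability tables. An AE entry or a listing line is still no substitute for a lab shift or a graded reaction by arm.

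Third, Day 84 shift tables are what Protocol 9.4.2 specifies. True, so the added lab column is an improvement and not the correction of a departure. The same section nevertheless says that abnormal values will be summarized, and the planned tables include no other lab table that would show an abnormal early-termination result.

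Fourth, no visit is scheduled between Day 1 and Day 14, so the day-5 case is hypothetical, and the specific wording of 6.10.4.1 could be read as overriding the general rule. That reading is possible, but 6.1.3 grants no exception, and a programmer following it would drop the grade.

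Finally, a reader might infer that the rule makes the active arms look safer. That is not shown. The rule is the same in every arm, the SAP expects similar dropout, and Protocol 8.2.3 says that the vehicle itself may irritate.

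**Conclusion.** The concern holds in a limited form and should be corrected. As written, SAP 6.1.3 removes from the lab summary and shift tables any subject whose only post-dose labs come from an early-termination or unscheduled visit on or before study day 70 or after day 98. It also conflicts with SAP 6.10.4.1 by excluding extra-visit tolerability grades before day 9 or in a window that already has scheduled data.

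The size is unknown. The 30–65 (no return) and 15–32 (half return) of 360 rest on an assumed 10–20% dropout, even timing and a sample at each withdrawal. The certain effect is under-reporting in whichever arm has these results. The Day 28 omission is a minor, separate error and adds no weight to the windowing point.

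**What to change.** 1. In SAP 6.1.3, state that the early-termination and unscheduled-visit exclusions apply only to by-visit summaries.
2. Add a last (or worst) post-baseline column to the lab shift tables (14.3.1.2.1.2, 14.3.1.2.2.2, 14.3.1.2.3.2), using every result after first application, and show days since last application. With one scheduled post-baseline lab, last and worst will mostly coincide, so one column is enough.
3. Derive Tables 14.3.0.2.2 and 14.3.0.2.3 from all post-application grades, whatever the visit type or study day, and say so in SAP 6.10.4.1.
4. Separately, add the Day 28 pre- and post-dose rows to Table 14.3.0.2.1.

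The cost is SAP wording, a table column and some programming; no new data are needed. The downside is that the added lab column mixes on- and off-treatment samples, which is why days since last application should be shown.
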